Despite their widespread use and current status as the most effective available resource, a meta-analysis combining individual participant-level data from 6,713 individuals from 17 randomized clinical trials underscored the small effect sizes associated with BMIs and indicated a “need for the development of more effective intervention strategies” (Huh et al., 2015). Further, a review of interventions for college student drinking noted that “significant enhancement of personalized feedback intervention efficacy has not been observed in over 15 years of study” (Miller, Meier, Lombardi & Leffingwell, 2015). A second major limitation is that prevention and intervention programs for college students historically focused exclusively on alcohol. Rates of anxiety and other mental health challenges have also been rising in college students and it is inefficient to have programs that do not comprehensively address mental health. A challenge for college student mental health providers is that college students rarely want to engage in “prevention programming”. Resources on college campuses often go under-utilized. We propose to develop a program for college students that will capitalize on the element of current prevention programming that appears to be most critical to effectiveness: the delivery of personalized feedback to stimulate change (Cronce, Bittinger, Liu & Kilmer, 2014). However, rather than focusing feedback on current patterns of alcohol use, we will provide personalized feedback on underlying dispositional factors known to be related to substance use and other mental health challenges, along with personalized recommendations and resource information tailored to the individual’s profile(s). In this way, we will utilize findings from the basic epidemiological literature about the key personality pathways that influence substance use and mental health to create a Personalized Feedback Program for each student. Importantly, each of the personality-related dimensions for which we will give feedback has positive features in addition to potential challenges. Our intervention will shift the focus from the provision of information about relative levels of substance use (what is currently provided), and provide information about personality profiles that can contribute to health and wellness. This will help students understand the potential strengths associated with their personalized profiles, along with potential challenges and give them personalized resources. In this way, we aim to address several limitations of the current literature, by focusing on something likely to be of greater interest to students (personality) in order to provide information about resources that can support them in their college experience.

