The focus of the present (minimal risk) study is to conduct a preliminary test of efficacy of our newly developed innovative prevention intervention, the Personalized Feedback Program (PFP) for college students. As such, participants will only be included in the present study if they are a full-time college student. Alcohol intervention programming is generally designed for traditional college students attending school full-time. This is not problematic since close to 80% of the incoming freshman class each year registers for at least 9 credits and is considered full-time. Currently the intervention is being developed with VCU students in mind and the resources provided are specific to VCU; thus, only VCU students will be eligible to participate. We are limiting the study to college freshmen on the premise that a college student's first year is the most effective time to intervene given the variability in quantity and

frequency of substance use among freshmen and the fact that the proportion of people who report drinking rises steadily across the college years. On most college campuses, substance prevention programs are delivered to incoming freshmen, before they are exposed to increased risk following the transition. Accordingly, we want to focus activities and outcome evaluation on freshmen to increase the potential for generalization to other college campuses. In addition, incoming freshmen are at greatest risk for problematic alcohol use and associated consequences. Our own work in Spif for Science and that of a previous study following a cohort of incoming freshmen also found that variables measured at entry to university are among the strongest predictors of substance use and problems. These findings underscore the importance of early intervention aimed at incoming freshmen, which is why we focus on this population. Students who are considered freshmen based upon credits (e.g., withdrew from courses during first year and did not meet credit requirements to be considered sophomores), will not be eligible, as they would comprise a unique group of likely high risk students. We will limit enrollment to freshmen over the age of 18. This should not be difficult because 98% of incoming VCU freshmen are 18-19 years of age.

[View: SF2 - Background, Rationale & Goals Section Complete](#)

Background, Rationale & Goals Section Complete

Protocol Progress:

- ❶ INITIAL SETUP
- ❷ BACKGROUND, RATIONALE & GOALS
- ❸ RESEARCH PLAN
- ❹ CONSENT PLAN

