PFP: In the PFP, students will answer items from the short UPPS-P Impulsive Behavior Scale (SUPPS-P; Lynam, 2013) which will measure impulsivity facets and the Big Five Inventory (BFI, John & Srivastava, 1999) which will estimate participant levels of extraversion vs introversion, conscientiousness vs. lack of direction and neuroticism vs. emotional stability. Based on their responses to these items, they will receive personalized feedback and campus resources to help them succeed during college. Further interactive elements in the program allow them to consider their goals, what could help them achieve those goals, and what may interfere. They are then guided through four sample scenarios where they can select different choice options and view their outcomes. See attached document "PFP" for the text included in the program.

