Control: The T1 post-program survey will ask questions pertaining to participants' satisfaction and experiences with the Resources Program. They will then be asked questions pertaining to their future intentions regarding campus resource use, and alcohol use and drug use, as well as their risk comprehension. See attached document "Immediate Post-Survey Control".

PFP: The T1 post-program survey will ask questions related to participants' satisfaction and experiences with the Personalized Feedback Program. They will then be asked questions pertaining to their future intentions regarding campus resource use, and alcohol use and drug use, as well as their risk comprehension. See attached document "Immediate Post-Survey PFP".

BMI: The T1 post-program survey will ask questions related to participants' satisfaction and experiences with the BMI Program. They will then be asked questions pertaining to their future intentions regarding campus resource use, and alcohol use and drug use, as well as their risk comprehension. See attached document "Immediate Post-Survey BMI".

PFP+BMI: The T1 post-program survey will ask questions related to participants' satisfaction and experiences with both the Personalized Feedback Program and the BMI Program. They will then be asked questions pertaining to their future intentions regarding campus resource use, and alcohol use and drug use, as well as their risk comprehension. See attached document "Immediate Post-Survey PFP+BMI".

T2 Survey: The T2 survey will be the same as the T3 survey. It will include items from the following validated measures: Mental Health Continuum-Short Form (MHC-SF; Keyes, 2009), Semi-Structured Assessment for the Genetics of Alcoholism (SSAGA; Bucholz et al., 1994), Alcohol Use Disorder Identification Test (AUDIT; Bohn, Babor, & Kranzler, 1995), Symptom Checklist-90 (SCL-90; Derogatis, Lipman, & Covi, 1973), and Alcohol: Stages of Change (Short Form) (Laforge, Maddock, & Rossi, 1998). These items will assess well-being, alcohol use/problems, drug use, current anxiety/depressive symptoms, and additional questions will be asked pertaining to utilization of campus

resources and risk comprehension. Additional items will be included to assess program usefulness.

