T3 Survey: The T3 survey will be the same as the T2 survey. It will include items from the following validated measures: Mental Health Continuum-Short Form (MHC-SF; Keyes, 2009), Semi-Structured Assessment for the Genetics of Alcoholism (SSAGA; Bucholz et al., 1994), Alcohol Use Disorder Identification Test (AUDIT; Bohn, Babor, & Kranzler, 1995), Symptom Checklist-90 (SCL-90; Derogatis, Lipman, & Covi, 1973), and Alcohol: Stages of Change (Short Form) (Laforge, Maddock, & Rossi, 1998). These items will assess well-being, alcohol use/problems, drug use, current anxiety/depressive symptoms, and additional questions will be asked pertaining to utilization of campus resources and risk comprehension. Additional items will be included to assess program usefulness.

Secondary Data Elements: Answers to the Spit for Science baseline survey will be incorporated as study baseline data as well. Data sharing will follow the same secure options previously described.

7. * The IRB only reviews research activities, so indicate which of the study activities are:

- Being performed exclusively for research purposes (i.e. they would not otherwise be done apart from this study) VERSUS.
- Alterations of routine activities/procedures (e.g. the study is altering the timing, frequency, method, location, amount, etc.) VERSUS.
- Being done for other purposes and whose data/results will be used secondarily in the study (e.g. standard medical or psychological tests, routine education practices, quality improvement initiatives, etc.).

This study is being performed exclusively for research purposes, though we anticipate that the findings will have important implications for substance use prevention on college campuses. The primary aim of this proposal is to conduct a preliminary test of efficacy of our newly developed innovative prevention intervention, the Personalized Feedback Program (PFP) for college students. Preliminary efficacy will be evaluated through a randomized controlled trial (RCT) comparing four conditions: assessment only controls, PFP, computer-delivered intervention based on brief motivational intervention (BMI) content/principles, and PFP+BMI.

8. If applicable, describe alternatives (research or non-research) that are available to potential participants if they choose not to participate in this study:

9. Upload any supporting tables or documents (e.g. protocol documents, figures/tables, data collection forms, study communications/reminders):

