We do not believe the study poses any additional risks to any specific population. The study investigators initially took a number of steps to ensure that all study materials would be acceptable to multiple groups and populations, and we will continue to make every effort to reduce any potential risks or harms to our participants. Our research team has extensive experience working with young adults and presenting findings in a manner that is useful to the population

being studied. Additionally, Co-I [name], Associate Director of the Health and Wellness Promotion Center ("The Well", changing to RecWell this upcoming year) at VCU, was instrumental in designing both the Personalized Feedback Program and the computer-delivered intervention based on BMI content/principles and selecting their language. She will continue to play a role in presenting the findings in a positive and empowering way to students. She has worked with students for over 5 years in the Well at VCU, worked in a similar role for 5 years at another university, and is highly adept at working with and conducting outreach for this population.

Within the Personalized Feedback Program, the names of all personality types were specifically chosen to reduce any stigma traditionally associated with that trait. All personality types start with "the good" things about them, and we emphasize that there are pros and cons associated with each of the different types. While we will be informed by students' generated personality types when looking at differences in response to the intervention and behavior changes following the intervention, we will not be presenting these findings in a derogatory way.

We intend for our recruitment methods to ensure we have a diverse sample of students with varying traits.

4. Where appropriate, discuss provisions for ensuring necessary medical, professional, or psychological intervention in the event of adverse events to the subjects:

The goal of this project is to ensure that all college students who complete the Personalized Feedback Program will receive adequate feedback and information about university resources that can support them. Participants will be encouraged to reach out to their university counseling/health services if they experience distress during the study.

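### Does looking at response by PFP-generated personality type commit the trial to a comparison that cannot show for whom the PFP works?

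*Protocol*

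**What the plan says.** The sentence at issue is in the protocol, Risks, Discomforts, Potential Harms and Monitoring, question 3, which asks about findings that could stigmatise a group. The answer says the team will be informed by "generated personality types when looking at differences in response to the intervention and behavior changes following the intervention", and promises that the results will not be presented in a demeaning way.

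Other passages bear on it:

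- **Source of the types.** Study Procedures, question 6: "In the PFP, students will answer items from the short UPPS-P Impulsive Behavior Scale", together with Big Five items. Under Behavioral Intervention Details, only the PFP and PFP+BMI arms complete the programme.
- **Other arms at T1.** Controls receive a resource list. BMI students answer BASICS and AUDIT items. The T1 post-program survey covers satisfaction and "questions pertaining to their future intentions regarding campus resource use, and alcohol use and drug use, as well as their risk comprehension". No personality instrument is named.
- **T2 and T3, all arms.** "These items will assess well-being, alcohol use/problems, drug use, current anxiety/depressive symptoms", plus resource use, risk comprehension and program usefulness. Neither personality scale is listed.
- **Baseline, all arms.** "Answers to the Spit for Science baseline survey will be incorporated as study baseline data as well". The instruments in that survey are not listed.
- **Premises.** Background, Rationale and Goals, question 1, describes feedback on "underlying dispositional factors known to be related to substance use and other mental health challenges". Study Population, question 7, says that "variables measured at entry to university are among the strongest predictors of substance use and problems".

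**The concern.** The PFP rests on feedback about traits, so a result split by personality type is easily read as showing for whom it works. Yet every student with a generated type received the PFP, and type is not randomised. The protocol itself says these traits go with substance use. Impulsive students, for example, could drink more, or increase their drinking faster over the first semester, with the PFP doing nothing. In the PFP arms alone, that pattern cannot be told apart from a weaker PFP effect in that type. Baseline data on use deal with a stable gap but not with types that follow different courses. At stake is a false claim of differential benefit in a secondary analysis.

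**Working it through.** **1. Sample.** 4 arms × 100 = 400 enrolled, as the protocol states. The target of 300 retained implies 25% loss (1 − 300/400), or 75 per arm if losses are equal, so 2 × 75 = 150 PFP-exposed students. Study Population, question 3, gives no effect size, SD or power. Everything below except the sample size is therefore assumed: normal outcome with SD 1, baseline-to-follow-up correlation r of 0.5 to 0.7, and one type against the rest (75 v 75, or 45 v 105).

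**2. Change score between types, PFP arms only, no programme effect.** The wording refers to behaviour change, so this is the natural analysis to check.

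- SD of change = √(2(1 − r)) = 1.00 at r = 0.5 and 0.775 at r = 0.7.
- SE = √(1/n₁ + 1/n₂) × SD of change. For 75 v 75 this is 0.163 and 0.126; for 45 v 105 at r = 0.5 it is 0.178.
- Rejection rate ≈ Φ(δ/SE − 1.96), where δ is the widening of the gap.
- Stable gap (δ = 0): 5%; simulated 4.6-5.2%.
- δ = 0.2, 75 v 75: 0.2/0.163 = 1.22, giving Φ(−0.74) = 0.23; 0.2/0.126 = 1.58, giving Φ(−0.38) = 0.35.
- δ = 0.2, 45 v 105, r = 0.5: 0.2/0.178 = 1.12, giving Φ(−0.84) = 0.20.
- Simulated, with a baseline gap of 0.3 SD: 9-12%, 20-35% and 39-65% for widening of 0.1, 0.2 and 0.3 SD.

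**3. Follow-up adjusted for baseline.** The gap left after adjustment is the follow-up gap − r × the baseline gap.

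- Stable gap of 0.3 SD at r = 0.5: 0.3 − 0.15 = 0.15. SE = 0.163 × √(1 − 0.25) = 0.141. 0.15/0.141 = 1.06, giving Φ(−0.90) = 0.18. Simulated range over the settings: 11-18%.
- The same 0.3 SD gap widening by 0.2 SD: simulated 60-69%.

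**4. Arm-by-type interaction, 150 PFP-exposed against 150 not.** This needs the trait in all four arms.

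- False-positive rate: about 5% in every scenario tested, including widening by 0.2 and 0.3 SD.
- SE = √(2(1/n₁ + 1/n₂)) × √(1 − r²), without the last factor if unadjusted. For 75 v 75 unadjusted: 0.231.
- Power at 0.3 SD: 0.3/0.231 = 1.30, giving about 0.255. Over both splits it is 22-25% unadjusted and 28-44% adjusted for baseline.
- 80% power needs 2.80 × SE, which is 0.46-0.61 SD even after adjustment.

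**5. What the text supports.**

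- The link between traits and use in the Background concerns level, which a change score handles.
- The entry variables in Study Population, question 7, are not named as personality traits.
- The phrase "before they are exposed to increased risk following the transition" explains why campuses deliver prevention to incoming students. It describes all freshmen, not one type against another.

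The inflation that survives a change score therefore rests on diverging courses that no passage states.

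**The case for a change.** The strongest case for a change is that the protocol announces a by-type look at behaviour change and expects to present findings from it. It names types generated by the programme, not registry traits, and these have no unexposed comparator. The identification failure does not depend on the size of any assumed gap. One sentence, with no new data, would close it: use a trait measured in all four arms and an exploratory interaction, or otherwise describe only. Low power is no reason to prefer a comparison that cannot identify the effect.

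The identification argument stands. A difference between types confined to PFP-exposed students does not show a differential PFP effect.

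What does not stand is the step from there to an error in the protocol. The sentence names no test, outcome, set of arms or contrast, and makes no causal claim. It is compatible with describing satisfaction by type, with comparing PFP+BMI against PFP within type (a valid randomised contrast for the added BMI), and with plain description. The proposed fallback of describing only contradicts nothing in the text. The interaction is possible only if the Spit for Science survey carries suitable trait items. That survey is not shown, and the protocol neither states nor excludes them. If it does carry them, they predate randomisation and are already available to the study.

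**Conclusion.** No change to the protocol follows. This is a passing remark whose analytic detail is left open, and a competent analyst fills that gap in the statistical analysis plan, which was not available here. No stated rule produces a wrong result, and Hypotheses 1 and 2 are unaffected.

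A conditional caution remains. If by-type differences in use, or in change in use, among PFP-exposed students are later read as showing for whom the PFP works, the data cannot support that reading. Such a claim would need a comparison with students who did not receive the PFP, on a trait measured before randomisation in all arms and with baseline use taken into account. Without such a measure, by-type results are descriptive.

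The size depends on assumptions. A change score keeps its 5% error rate under a stable gap, and rejects in 20-35% of trials if a 0.3 SD gap widens by 0.2 SD with no programme effect. The gaps, correlations, type shares and normal outcome are all assumed, and the several trait dimensions are reduced to one type against the rest. Even the sound alternative would have only 22-44% power for a 0.3 SD interaction, so writing it into the protocol would gain little.
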